## Objective:

To determine if different techniques used in the creation of suture anchor socket creation can influence post-op pain following rotator cuff repair

## Hypothesis:

We propose that the use of an arthroscopic drill for creation of anchor socket will result in less pain post-operatively when compared to the use of the punch.

## Clinical significance:

Arthroscopic rotator cuff repair has become a mainstay of treatment for rotator cuff tears requiring surgical intervention and has been reported to decrease pain and increase function to levels similar to open approaches while requiring smaller incisions and less soft

tissue disruption. Development of reliable and effective procedure-specific instrumentation, primarily in the form of suture anchor systems, has been a key reason for the successful progression in arthroscopic rotator cuff repair.

Even with advanced instrumentation, it has become evident that a subset of patients experience pain and functional limitations in the acute post-operative period. Studies have demonstrated that rotator cuff tear size does not correlate with post-operative pain in patients, and that pain scores may not be improved by using an arthroscopic repair versus an open repair. Austin et. al. observed that 56 patients having undergone rotator cuff repair for full thickness rotator cuff tears suffered sleep disturbances for up to 3 months after surgery. The causes for increased post-operative pain in patients following rotator cuff repair remain poorly understood. As such, all relevant variables, including technical components of the repair, should be critically evaluated in an effort to optimally address post-operative pain for patients.

Because arthroscopic rotator cuff repair most commonly uses suture anchors inserted into proximal humeral bone to re-attach tendon(s), the authors sought to examine technical components of suture anchor insertion. The sockets for insertion of suture anchors used in rotator cuff repair are made most often with use of a surgical punch that, in theory, corticates the socket to optimize anchor thread purchase and pull-out strength. However, use of a punch may cause significant micro-trauma to proximal humeral bone as it fractures trabeculae to create the socket, as opposed to use of a drill bit which cuts and removes trabeculae to create the socket. These fractures occurring as the result of stress-induced microtrauma to bone have a well-documented role in causing pain. These microfractures are also associated with bone marrow lesions seen on MRI. Importantly, bone marrow lesions in the greater tuberosity have been reported to occur after arthroscopic rotator cuff repair using punch-socket suture anchors, and can remain present for 6 – 12 months. Taken together, these findings give credence to the theory that punch-induced microfractures may contribute to postoperative pain after arthroscopic rotator cuff repair.

### **Study Design:**

- Randomized prospective cohort study.
- 1. Inclusion criteria
  - a. Patient's aged 18-80 years old with diagnosis of rotator cuff tear having failed non-operative management and being indicated for surgical intervention with use of suture anchors.
- 2. Exclusion criteria
  - a. Glenohumeral arthrosis
  - b. Previous shoulder surgery
  - c. Psychiatric diseases
  - d. Rheumatologic diseases
  - e. Fibromyalgia
  - f. Spine diseases
- 50 Patients will be randomized to have bone sockets formed with either a punch (25) or a drill (25) at the time of surgery.
- Patients will follow up at their standard of care visits at 2 weeks, 6 weeks, 3 months, and 6 months
- PROMIS SF v2.0 – Physical Function 10a, PROMIS SF v1.0 – Pain Interference 6a, SANE, ASES, VAS scores will be collected at each visit for research purposes.

- Patients will record their pain levels and number of pain pills they took for three days post-op for research purposes.
- MRI of the shoulder of the first 5 patients in each group will be obtained at 2 weeks post-op for evaluation of bone marrow edema pattern in the proximal humerus for research purposes.

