**Possible risks to research patients:**

Potential for loss of confidentiality. Each patient will be assigned a random subject number. The key linking numbers to subjects will be locked away in the offices of University of Missouri, Missouri Orthopedic Institute. All published information will be through de-identified subject numbers. The key linking the patient and all identifiable personal information will be destroyed 10 years post-study completion to allow for complete data analysis and use of data for publication writing.

Patients will be randomized 1:1 into either the punch or drill. The surgeon does not determine the procedure; there is always the potential risk that the other procedure may result in more post-op pain.

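### No pre-operative score is scheduled for any of the five patient-reported instruments, so a comparison of 25 versus 25 cannot be adjusted for baseline

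*Protocol*

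**What the plan says.** The Study Design section of the protocol fixes the size of the trial: "50 Patients will be randomized to have bone sockets formed with either a punch (25) or a drill (25) at the time of surgery". It then gives the visit schedule: "Patients will follow up at their standard of care visits at 2 weeks, 6 weeks, 3 months, and 6 months". The next bullet names PROMIS Physical Function, PROMIS Pain Interference and three further scores, and sets their timing: "SANE, ASES, VAS scores will be collected at each visit for research purposes".

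Two other kinds of data are planned, both after surgery. Patients are to "record their pain levels and number of pain pills they took for three days post-op", and the first five patients in each arm have an MRI two weeks after the operation.

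The Hypothesis section states that the drill "will result in less pain post-operatively when compared to the use of the punch". The section on possible risks repeats the allocation: "Patients will be randomized 1:1 into either the punch or drill".

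No section schedules a screening, baseline or pre-operative measurement of any instrument, or says that scores from routine records will be used as study data.

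**The concern.** In a small randomized trial with a patient-reported outcome, the same score taken before treatment is usually among the cheapest sources of precision. It explains part of the between-patient variation and removes that part from the comparison of the arms. As scheduled, the trial has no such score for any of its five instruments. It therefore allows neither a comparison adjusted for the pre-operative score nor an analysis of change from baseline, and a chance difference between the arms in pre-operative pain or function could be neither seen nor corrected.

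Which data are collected, and when, is settled by the protocol. A statistical analysis plan can choose a model, but it cannot supply a score that was not taken, and once a patient has had surgery the opportunity is gone.

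**Working it through.** **Reading the schedule.** The bullet that ties the instruments to each visit directly follows the bullet listing the visits at 2 weeks, 6 weeks, 3 months and 6 months. Those four are the only visits in the protocol and the natural reference. The diary and the MRI are expressly post-operative.

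**Inputs.** From the protocol: n = 25 per arm, N = 50, 1:1. The protocol gives no alpha, power, effect size, SD or pre/post correlation, so its figure of 50 cannot be reproduced. Assumed here: two-sided alpha 0.05, 80% power, outcome SD of 1 (differences are in SD units), complete follow-up, and correlation r between pre- and post-operative score of 0.2, 0.3, 0.5 or 0.7.

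**Unadjusted comparison.** The standard error of the difference is √(2/25) = 0.283 SD. By normal approximation the detectable difference is (1.960 + 0.842) × 0.283 = 0.79 SD. By the two-sample t test with 48 degrees of freedom it is 0.809 SD. Power for a true difference of 0.6 SD is 54.7%.

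**Adjusted comparison.** With the pre-operative score as a single covariate, the variance is multiplied by (1 − r²) × (1 + 1/46). Here 1/46 = 1/(N − 4) is the cost of estimating the covariate's slope, and the test has 47 degrees of freedom. For r = 0.5 the factor is 0.75 × 1.0217 = 0.766. The equivalent number of patients is 50 divided by the factor; for r = 0.5, 50/0.766 is about 65.

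| r | Variance factor | Variance saved | Detectable difference (SD) | Equivalent patients | Power at 0.6 SD |
|---|---|---|---|---|---|
| unadjusted | 1 | – | 0.809 | 50 | 54.7% |
| 0.2 | 0.981 | 2% | 0.801 | 51 | 55.5% |
| 0.3 | 0.930 | 7% | 0.780 | 54 | 57.7% |
| 0.5 | 0.766 | 23% | 0.708 | 65 | 66.0% |
| 0.7 | 0.521 | 48% | 0.584 | 96 | 82.1% |

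Simulation with 20,000 trials per value of r gave variance ratios of 0.986, 0.923, 0.765 and 0.520, in line with the formula.

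**Break-even.** The factor equals 1 when (1 − r²) × 47/46 = 1, so r = √(1/47) = 0.146. Below that, adjustment costs slightly more than it saves: at r = 0.1 the detectable difference is 0.814 SD.

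**Chance imbalance.** The pre-operative difference between arms has standard deviation 0.283 SD. An imbalance above 0.3 SD in either direction therefore occurs in 2 × [1 − Φ(0.3/0.283)] = 28.9% of trials of this size. Only the fraction r of it carries into the outcome: 0.3 × r = 0.06, 0.09, 0.15 or 0.21 SD for the four values of r. This is another view of the variance already counted in the table, not a further loss.

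**The case against.** The strongest reply is that nothing here is invalid. The hypothesis concerns post-operative pain between arms, not change from baseline. Randomization makes the scheduled comparison unbiased, and its standard error already allows for chance imbalance. This stands, and it limits the point to precision.

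Second, the benefit depends on a correlation the protocol does not give. At r = 0.2 it is worth one patient and at r = 0.3 about four; the attractive figures need 0.5 or more. This also stands, and is why a range is shown. The gain is least certain for the three-day diary: pill count has no pre-operative counterpart among the five instruments, and the diary's pain scale is not stated. The figures apply to the visit scores.

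Third, the wording on each visit might loosely include a pre-operative clinic visit, since patients must already have been found to need surgery, and routine records may hold scores. This is possible, but no such visit is listed, and nothing ensures that all five instruments exist for all 50 patients. If it was intended, the protocol still needs a line saying so.

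Finally, a later analysis could adjust for other pre-treatment characteristics, such as age. That is true; what is lost is adjustment for the pre-operative score of the instrument itself.

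**Conclusion.** The point holds as a loss of precision, not a source of bias. As written, the schedule yields no pre-operative score for any instrument, and the loss is permanent for each patient once operated on. Under the assumptions above, the cost ranges from almost nothing (0.81 against 0.80 SD detectable at r = 0.2) to substantial (0.81 against 0.58 SD at r = 0.7). At r = 0.5 the missing score is worth about 15 patients in a trial of 50 (65 − 50). The reading of the schedule is the natural one but not the only possible one, and the size of the gain rests wholly on r. The change is worth making because it is cheap and the sample is small.

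**What to change.** In Study Design, add one collection of the same five instruments before surgery and before the allocation is known, and state that each pre-operative score will be the covariate in the between-arm comparison of that instrument. If routine pre-operative scores are meant to serve, say so and name them as study data for all patients. Details of the model can be left to the statistical analysis plan.

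The cost is one line in the protocol and one extra questionnaire set, a few minutes per patient, with no additional patients or procedures. The downside is little or no gain if the correlation proves to be below about 0.2.

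### The three-day pill count is an outcome, but pre-operative analgesic use is neither an eligibility condition nor recorded, which costs precision and makes the counts harder to read

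*Protocol*

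**What the plan says.** The diary item, in Protocol, Study Design, reads: "Patients will record their pain levels and number of pain pills they took for three days post-op for research purposes". It is a plain number of pills. Drug, strength, and whether a tablet was already part of the patient's routine are not mentioned.

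The inclusion criterion admits adults with a cuff tear "having failed non-operative management and being indicated for surgical intervention with use of suture anchors". It sets no condition on analgesic use. There are six exclusions. Two concern the joint (arthrosis and earlier shoulder surgery). The other four are "Psychiatric diseases", "Rheumatologic diseases", "Fibromyalgia" and "Spine diseases". None concerns opioids or other analgesics.

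All listed data collection follows surgery: the three-day diary, the MRI subset at 2 weeks, and questionnaires at 2 weeks, 6 weeks, 3 months and 6 months. On allocation the section says "50 Patients will be randomized to have bone sockets formed with either a punch (25) or a drill (25) at the time of surgery". Possible risks to research patients gives the ratio as 1:1. No stratification factor is stated in either place.

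**The concern.** The last four exclusions are conditions that can affect pain, while the most direct influence on a count of pain tablets, namely what the patient was already taking, is left open. The population makes prior use plausible: these patients reach surgery after non-operative treatment has failed, and someone taking analgesics for the cuff tear itself is not removed by any listed exclusion.

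If such patients record all the analgesics they take, their counts contain a part that has nothing to do with the socket technique. Habitual opioid users may also need more after surgery with either tool. At stake is the precision of one of only two measures taken before 2 weeks, in a trial with 25 patients per arm. The meaning of the count is also at stake, since a difference in pills could reflect habit, drug or strength rather than new pain. A statistical analysis plan cannot adjust for prior use from the data that the protocol plans to collect, so this belongs in the protocol.

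**Working it through.** The protocol states no SD, effect size, power or prevalence of prior use, so there is no planned figure to reproduce. The check has two parts: what the plan would collect, and how large the loss could be under stated assumptions.

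**What would be collected.** Eligibility sets no condition on analgesics. Every listed data item is post-operative. The diary gives a number of pills without drug or type. Taken together, the planned data contain nothing from which prior use could be derived.

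**Inputs.** From Study Design: 25 per arm. Assumed: share of prior users p = 10% to 30%; extra pills taken by a prior user d = 0.5 to 2 SD, where SD is that of patients without prior use and is taken to be the same within both groups.

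**Variance.** By the law of total variance, ignoring prior use gives a count with variance SD² × [1 + p(1 − p)d²]. The standard error of the difference between arms rises by the square root of the bracket.

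| p | d | 1 + p(1 − p)d² | Square root |
|---|---|---|---|
| 0.1 | 0.5 | 1 + 0.09 × 0.25 = 1.02 | 1.01 |
| 0.2 | 0.5 | 1 + 0.16 × 0.25 = 1.04 | 1.02 |
| 0.1 | 1 | 1 + 0.09 × 1 = 1.09 | 1.04 |
| 0.2 | 1.5 | 1 + 0.16 × 2.25 = 1.36 | 1.17 |
| 0.3 | 2 | 1 + 0.21 × 4 = 1.84 | 1.36 |

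**Power.** As a yardstick, 25 per arm gives 80% power (two-sided 5%, t-test) for a difference of 0.81 SD when there are no prior users. Dividing 0.81 by the square roots in the last three rows reduces power to about 77%, 67% and 54%.

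**Error rate.** Simulating two arms of 25 with no true difference, under the assumptions of those same three rows, the unadjusted t-test rejects in 4.8% to 5.2% of trials. The nominal 5% is kept.

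**Imbalance.** With independent Binomial(25, p) counts of users, the chance that the arms differ by 4 or more is 9.6%, 21.3% and 27.9% at p = 10%, 20% and 30%. A difference of 4 users shifts the difference in means by (4/25) × d, for example 0.16 SD at d = 1 and 0.32 SD at d = 2. This is the same sampling variation that the variance factor already expresses, so it is an illustration and not a second harm to add.

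**What the covariate recovers.** Under these assumptions, fitting prior use (yes/no) removes the term p(1 − p)d² and returns the residual variance to SD², for one degree of freedom.

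**The case against.** The strongest reply is that randomisation already protects the comparison. It does: prior use is balanced in expectation and the test keeps its level. A reader might infer from the imbalance figures that prior users can bias the result or produce spurious differences beyond the nominal error rate. Neither the design nor the simulation supports that.

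A reader might also infer that habitual tablets are certainly counted as post-operative need. The protocol does not say so. It leaves undefined whether the count covers only pills prescribed after surgery or all analgesics. That is a gap in the diary item, and the remedy has to close it too.

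Three further objections stand in part:

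- The size is wholly assumed, and 84% needs both extremes together; at 20% users and 0.5 SD the variance rises by only 4%.
- The hypothesis concerns pain, so the diary pain level is closer to it than the pill count. No primary outcome is named, and VAS, ASES and Pain Interference are also collected at four visits.
- The protocol gives no reason for its exclusions, and admitting analgesic users is a defensible broad-eligibility choice, not a contradiction.

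The objection that adjustment can be left to an analysis plan does not dispose of the point, because the covariate must first be collected. Medication history may exist in clinical charts, so it would be too strong to say that prior use could never be recovered. The protocol simply does not plan to obtain it.

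**Conclusion.** The point holds as an avoidable loss of precision and interpretability on one early outcome. It is not a bias, and it does not threaten the validity of the randomised comparison. If 10% to 30% of patients are prior users taking 0.5 to 2 SD more pills, the variance of the count rises by about 2% to 84% and the standard error by about 1% to 36%. At the low end this is negligible; from the middle of the range (20% users, 1.5 SD, standard error up 17%) it matters with 25 per arm. Which end applies cannot be told from the protocol. The range also supposes that habitual pills are at least partly recorded in the diary, which the wording permits but does not establish. The documents do not support reading the eligibility list as an error or as inconsistent with itself.

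**What to change.** Three additions to Study Design:

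1. At enrolment, before surgery, record regular opioid and other analgesic use (yes/no and type). Asking beforehand avoids recall influenced by the operation and its result.
2. State which pills the diary count covers, and have patients identify which pills they took, so that habitual and new use and different drugs can be told apart.
3. Name pre-operative use as a prespecified covariate for the three-day pill count and the diary pain level. The model itself can be left to the analysis plan.

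Stratifying allocation by prior use is optional. Excluding prior users is not needed; it would narrow the population and could slow accrual.

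The cost is one enrolment question, a slightly longer diary entry and one degree of freedom.

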**Training in the policies protecting the rights and welfare of human subjects in research:**

All staff involved in this study has had IRB-approved training according to The University of Missouri Healthcare guidelines

**Publication of private information:**

Investigators intend to publish the results of this study without identifying the subjects; and every attempt will be made to follow strict confidentiality. The results of this research may appear in scientific publications without identifying the patients.

**Future contact with research patients:**

Research patients/caregivers may be contacted to participate in future research.

**Possible risks to research patients:**

Potential for loss of confidentiality. Each patient will be assigned a random subject number. The key linking numbers to subjects will be locked away in the offices of University of Missouri, Missouri Orthopedic Institute. All published information will be through de-identified subject numbers. The key linking the patient and all identifiable personal information will be destroyed 10 years post-study completion to allow for complete data analysis and use of data for publication writing.

Patients will be randomized 1:1 into either the punch or drill. The surgeon does not determine the procedure; there is always the potential risk that the other procedure may result in more post-op pain.

**Possible benefits:**

Research patients enrolled in the study will not benefit directly from this study itself; however, information gained from this study could benefit patients being treated in the future. Specifically it may help determine a new standard of care for patients with upper extremity injuries with resultant hand stiffness.

**Costs to subjects:**

No costs will be incurred by the subjects above and beyond the standard medical practice.

